1. SYNOPSIS

Protocol Title:	A Randomized, Double-Blind, Placebo-Controlled, Parallel-Group Study to Evaluate the Efficacy and Safety of Intravenously Administered BIIB092 in Participants with Progressive Supranuclear Palsy
Protocol Number:	251PP301
Version Number:	7
Name of Study Treatment:	BIIB092
Study Phase:	2b
Study Indication:	Progressive Supranuclear Palsy
Study Rationale:	
The neuropathological hallmark of Progressive Supranuclear Palsy (PSP) is the presence of tau pathology in characteristic subcortical and cortical brain regions. N-terminal tau is implicated in mediating the transcellular spreading of this tau pathology in PSP.
 
Based on the available preclinical and clinical data, BIIB092 (formerly known as BMS-986168 and IPN007) is expected to prevent spreading of tau pathology by binding and reducing unbound N-terminal tau in brain interstitial fluid, thereby delaying the progression of clinical signs and symptoms of PSP. The purpose of this study is to demonstrate the efficacy of BIIB092 in the treatment of PSP and characterize its safety/tolerability profile.

Study Objective(s) and Endpoints:	
The primary objectives of the study are to: 1) Evaluate the efficacy of BIIB092 and 2) Assess the safety and tolerability of BIIB092.
 
The primary endpoints that relate to these objectives are: 1) Change from baseline in the total PSP Rating Scale (PSPRS) score at Week 52 in participants treated with BIIB092 relative to the change in the total PSPRS score in participants treated with placebo and 2) Frequency of deaths, serious adverse events (SAEs), adverse events (AEs) leading to discontinuation, and Grade 3 & 4 laboratory abnormalities.
 
Key secondary objectives and endpoints are as follows:
 
• To evaluate the efficacy of BIIB092, compared to placebo, as measured by a change from baseline in the Movement Disorder

CONFIDENTIAL

The information contained herein may not be used, disclosed, or published without the written consent of Biogen MA Inc.

Society-sponsored revision of the Unified Parkinson's Disease Rating Scale (MDS-UPDRS) Part II at Week 52.

The impact of BIIB092 on the MDS-UPDRS Part II will be evaluated relative to the change from baseline at Week 52 of the BIIB092-treated participants to that of the placebo-treated participants.

- To evaluate the efficacy of BIIB092, compared to placebo, as measured by the Clinical Global Impression of Change (CGI-C) at Week 52.

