2 DESCRIPTION OF OBJECTIVES AND ENDPOINTS

The objectives and endpoints from the protocol Section 4 are described below.

| Objective | Endpoint |
|---|--|
| Primary | |
| To evaluate the efficacy of BIIB092, compared to placebo, as measured by a change from baseline in the PSP Rating Scale (PSPRS) at Week 52. | The primary efficacy endpoint will be evaluated by comparing the change from baseline in the total PSPRS score at Week 52 in participants treated with BIIB092 relative to the change from baseline in the total PSPRS score in participants treated with placebo. |
| To assess the safety and tolerability of BIIB092, relative to placebo, by measuring the frequency of deaths, SAEs, and AEs leading to discontinuation, and Grade 3 & 4 laboratory abnormalities. | The primary safety endpoint will be evaluated by tabulating the numbers and percentages of deaths and unique participants with SAEs and AEs leading to discontinuation, and Grade 3 & 4 laboratory abnormalities. |
| Key Secondary | |
| To evaluate the efficacy of BIIB092, compared to placebo, as measured by a change from baseline in the Movement Disorder Society-sponsored revision of the Unified Parkinson's Disease Rating Scale (MDS-UPDRS) Part II at Week 52. | The impact of BIIB092 on the MDS-UPDRS Part II will be evaluated relative to the change from baseline at Week 52 in the BIIB092-treated participants and compared to that of the placebo-treated participants. |
| To evaluate the efficacy of BIIB092, compared to placebo, as measured by the Clinical Global Impression of Change (CGI-C) at Week 52. | The impact of BIIB092 on the CGI-C scale score will be evaluated at Week 52 in the BIIB092-treated participants and compared to that of the placebo-treated participants. |
| To evaluate the efficacy of BIIB092, compared to placebo, as measured by a change from baseline in the Repeatable Battery for the Assessment of Neuropsychological Disease Severity (RBANS) at Week 52. | The impact of BIIB092 on the RBANS scale will be evaluated relative to the change from baseline at Week 52 in the BIIB092-treated participants and compared to that of the placebo-treated participants. |

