6.3 Clinical Laboratory Data

The following scheduled clinical laboratory parameters are to be assessed:

| | |
|--|---|
| Hematology | |
| Red blood cell count | |
| Hemoglobin | |
| Hematocrit | |
| Total leukocyte count, including differential | |
| Platelet count | |
| Serum Chemistry | |
| Aspartate aminotransferase (AST) | Total Protein |
| Alanine aminotransferase (ALT) | Albumin |
| Total bilirubin | Sodium |
| Direct bilirubin | Potassium |
| Alkaline phosphatase | Chloride |
| Lactate dehydrogenase (LDH) | Calcium |
| Creatinine | Phosphorus |
| Blood Urea Nitrogen (BUN) | Magnesium |
| Uric acid | Creatine kinase |
| Glucose | Thyroid stimulating hormone (TSH)- screening only |
| Urinalysis | |
| Protein | |
| Glucose | |
| Blood | |
| Leukocyte esterase | |
| Specific gravity | |
| pH | |
| Microscopic examination of the sediment if blood, protein or leukocyte esterase are positive on the dipstick | |
| Serology | |
| Serum for hepatitis C antibody, hepatitis B surface antigen (screening only) | |
| Other Analyses | |

| |
|--|
| INR |
| Prothrombin Time |
| Hemoglobin A1C (HbA1C)- screening only |
| Pregnancy test (WOCBP only: screening, predose, discharge). |
| Follicle stimulating hormone (FSH) (screening only for women only) |

Summaries of clinical laboratory data will be performed for scheduled laboratory parameters only. Listings of individual laboratory measurements by subjects for all the parameters, both scheduled and unscheduled, will be provided.

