6.3.2 Qualitative analyses

For all qualitative analyses, all values will be included (not just the “analyzed record” within each visit window in the quantitative analyses).

Shift analyses

Laboratory data will be summarized using shift tables where appropriate. Each subject’s hematology, blood chemistry, coagulation and urinalysis (excluding microscopic examination) values will be flagged as “low”, “normal”, or “high” relative to the normal ranges of the central laboratory or as “unknown” if no result is available. Each subject’s urinalysis values for protein, glucose, blood, and leukocyte esterase will be flagged as “abnormal” if positive, “normal” if negative, or “unknown” if no value is available.

For each parameter, the analysis will be based on subjects with at least one post-baseline value. Shifts from baseline to high/low status will be presented for hematology, blood chemistry, coagulation and urinalysis (specific gravity and pH), and shifts from baseline to abnormal (or unknown to abnormal) will be presented for urinalysis parameters (protein, glucose, blood, and leukocyte esterase). Shift to low includes normal to low, high to low, and unknown to low; shift to high includes normal to high, low to high, and unknown to high. Subjects need to have at least one post-baseline evaluation and a baseline value either unknown or not low/high/abnormal in order to be included in the analysis.

Grade analyses

Each scheduled laboratory parameter will be summarized both by worst post-baseline grade and by worst cumulative post-baseline grade; this analysis includes the primary endpoints of Grade 3 and 4 laboratory abnormalities. Subjects need to have at least one post-baseline evaluation in order to be included in the analysis. Common Terminology Criteria for Adverse Events v4.0.3 (CTCAE) published on 14 June 2010 will be used for grade determination. Grade determination is based solely on laboratory values and does not take other clinical information into account; therefore, a lower grade may be assigned to a laboratory parameter result since clinical information does not contribute to the grading assessment. Thus, the incidence of higher grades may be underestimated.

For calcium (mmol/L), the laboratory result will be corrected by the concurrent albumin (g/L) result for CTCAE grade determination. The derivation of the corrected calcium (mmol/L) will be derived as follows:

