$$\text{Corrected calcium (mmol/L)} = \frac{1}{4} * [\text{calcium(mmol/L)} - 0.8 * (0.1 * \text{albumin(g/L)} - 4)]$$

Potentially Clinically Significant laboratory abnormalities analyses

For hematology, blood chemistry and urinalysis, the number of subjects with potentially clinically significant (PCS) laboratory abnormalities post-baseline will be summarized for the parameters provided in Table 9, which also shows the thresholds used to determine PCS results. Subjects need

to have at least one post-baseline evaluation and a baseline value not PCS (including missing) in order to be included in the analysis. A listing will be provided for subjects with any PCS result post-baseline.

Table 9 Criteria to Determine Potentially Clinically Significant (PCS) Laboratory Abnormalities

| Clinical Laboratory Outlier Criteria | | |
|---|----------------------------|----------------------------|
| Parameter name | PCS Low | PCS High |
| HEMATOLOGY | | |
| White blood cells | <3.0 x 10 ⁹ /L | >16 x 10 ⁹ /L |
| Lymphocytes | <0.8 x 10 ⁹ /L | >12 x 10 ⁹ /L |
| Neutrophils | <1.5 x 10 ⁹ /L | >13.5 x 10 ⁹ /L |
| Monocytes | N/A | >2.5 x 10 ⁹ /L |
| Eosinophils | N/A | >1.6 x 10 ⁹ /L |
| Basophils | N/A | >1.6 x 10 ⁹ /L |
| Red blood cells | ≤3.5 x 10 ¹² /L | ≥6.4 x 10 ¹² /L |
| Hemoglobin - Females | ≤95 g/L | ≥175 g/L |
| Hemoglobin - Males | ≤115 g/L | ≥190 g/L |
| Hematocrit - Females | ≤0.32 L/L | ≥0.54 L/L |
| Hematocrit - Males | ≤0.37 L/L | ≥0.60 L/L |
| Platelet count | ≤75 x 10 ⁹ /L | ≥700 x 10 ⁹ /L |
| BLOOD CHEMISTRY | | |
| Alanine aminotransferase (ALT) | N/A | >3 x ULN |
| Aspartate aminotransferase (AST) | N/A | >3 x ULN |
| Alkaline phosphatase (ALP) | N/A | >3 x ULN |
| Total bilirubin | N/A | >1.5 x ULN |
| Blood urea nitrogen (BUN) | N/A | ≥10.7 mmol/L |
| Creatinine | N/A | ≥176.8 umol/L |
| Sodium | ≤126 mmol/L | ≥156 mmol/L |
| Potassium | ≤3 mmol/L | ≥6 mmol/L |
| Chloride | ≤90 mmol/L | ≥118 mmol/L |
| Glucose | ≤2.2 mmol/L | ≥9.7 mmol/L |
| Calcium | ≤2 mmol/L | ≥3 mmol/L |
| Phosphorus | ≤0.6 mmol/L | ≥1.7 mmol/L |
| Albumin | ≤25 g/L | ≥625 g/L |
| Total protein | ≤45 g/L | ≥100 g/L |
| URINALYSIS | | |
| Glucose | N/A | ≥ 1000 mg/dL |
| Protein | N/A | ≥ 100 mg/dL |
| ULN = upper limit of normal | | |

Potential serious hepatotoxicity

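### No planned table counts each participant once for Grade 3 or 4 laboratory abnormalities, although this is a component of the primary safety endpoint and on its natural reading calls for that count

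*SAP*

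**What the plan says.** Section 4 of the protocol and Section 2 of the placebo-controlled SAP set out how the primary safety endpoint is measured: "tabulating the numbers and percentages of deaths and unique participants with SAEs and AEs leading to discontinuation, and Grade 3 & 4 laboratory abnormalities". The protocol synopsis is looser: "Frequency of deaths, serious adverse events (SAEs), adverse events (AEs) leading to discontinuation, and Grade 3 & 4 laboratory abnormalities".

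The Grade analyses part of Section 6.3.2 of the placebo-controlled SAP is the only place where laboratory grades are analysed. It states "Each scheduled laboratory parameter will be summarized both by worst post-baseline grade and by worst cumulative post-baseline grade; this analysis includes the primary endpoints"; the endpoints meant are the Grade 3 and 4 laboratory abnormalities. Subjects need at least one post-baseline evaluation to be included, and grading uses CTCAE v4.0.3.

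The other laboratory outputs work differently:
- The shift tables in 6.3.2 are by parameter.
- The potentially clinically significant (PCS) analysis uses its own thresholds rather than CTCAE grades, and is also by parameter: "laboratory abnormalities post-baseline will be summarized for the parameters provided in Table 9".
- Section 6.3 promises subject-level data: "Listings of individual laboratory measurements by subjects for all the parameters, both scheduled and unscheduled, will be provided".

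The overall AE table in Section 6.2.2 has a subject count for SAEs and another for AEs leading to discontinuation. It has no laboratory-grade row. The open-label extension SAP describes no grade analysis.

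**The concern.** The endpoint sentence places the laboratory item in the same list as SAEs and AEs leading to discontinuation. Each of those two gets a row in which a subject counts once, whatever the number of events. The laboratory item gets one worst-grade table per parameter and no such row. *Worst* and *worst cumulative* both operate within a parameter, so neither collapses a participant's results across parameters.

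Two things are at stake. First, the report may carry no single figure for a component of the primary safety endpoint. A reader who adds the parameter rows to get one will count some participants several times. Second, if the figure is requested after unblinding, its definition (which parameters, which grades, which denominator) will be chosen with the data in view.

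**Working it through.** **Inputs.** Planned arm sizes are 306 BIIB092 and 153 placebo (Protocol 17.1). The plan states no Grade 3 or 4 rate, no number of gradable parameters and no test on laboratory grades, so there is no plan figure on this point to reproduce. The 80% power in Protocol 17.1 concerns PSPRS. It reproduces (80.2% to 80.4% with 230 and 115 completers, difference 3.2, SD 9.95) but plays no part here.

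**Can the participant count be recovered from the parameter tables?** Let x_j be the number of subjects in an arm who are Grade 3 or 4 on parameter j, and U the number who are Grade 3 or 4 on at least one. Then

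max(x_j) ≤ U ≤ min(sum of x_j, arm size).

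The tables fix the x_j but not the overlap between them, so U stays open within these bounds.

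*Constructed example.* Take 20 parameters, each showing 4/306 (1.3%) against 1/153 (0.7%); Fisher p = 0.67 for each row. The bounds on U are 4 to 80 on BIIB092 and 1 to 20 on placebo.

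| Overlap | BIIB092 | Placebo | Fisher p |
|---|---|---|---|
| No subject has two abnormal parameters | 80/306 = 26.1% | 20/153 = 13.1% | 0.001 |
| Each affected BIIB092 subject has exactly two; placebo none | 40/306 = 13.1% | 20/153 = 13.1% | 1.0 |

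The same 20 tables are compatible with a doubled proportion of affected participants and with no difference. The counts are invented, but the argument needs no assumption about true rates.

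**Which display is more sensitive?** These are illustrations only: rates are assumed, parameters independent, power is from a two-proportion normal approximation at two-sided 5%, and the any-parameter rate is 1 − (1 − p)^20 when all parameters share rate p.
- *Diffuse excess*, every parameter 0.5% on placebo and 1.0% on BIIB092: the any-parameter rates are 1 − 0.995^20 = 9.5% and 1 − 0.990^20 = 18.2%. Power is about 6% for one row and about 70% for the pooled row.
- *Excess in one parameter*, all at 0.5% except one at 5% on BIIB092: the any-parameter rates are 9.5% and 1 − 0.995^19 × 0.95 = 13.6%. Power is about 75% for that parameter's row and about 23% for the pooled row.

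The ordering reverses with the scenario, so neither display replaces the other.

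**Calcium.** As printed in 6.3.2, corrected calcium is ¼ × [calcium − 0.8 × (0.1 × albumin − 4)]. At albumin 40 g/L the correction term is 0.8 × (4 − 4) = 0, so the corrected value should equal the measured one. For calcium 2.4 mmol/L the formula gives 2.4/4 = 0.6 mmol/L, against a PCS low limit of 2 mmol/L in Table 9 of the same SAP. The factor ¼ appears to fall on a calcium value already in mmol/L. This may be an artefact of text extraction.

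**The case against.** The strongest objection is that the endpoint sentence is ambiguous. The phrase about unique participants attaches directly to SAEs and AEs leading to discontinuation. The laboratory item follows a comma, the synopsis speaks only of frequency, and 6.3.2 uses the plural for the laboratory endpoints. On a per-parameter reading, a worst-grade table counts each subject once within a parameter and the endpoint is produced. This stands as a limit on the point. A reader might infer that the planned tables can never yield the endpoint; the documents support that only on the any-parameter reading. I find that reading the more natural, because two neighbouring items in the list get an any-event subject row, but the text does not settle it.

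A second objection is that little would be hidden. Under Protocol 10.6, laboratory results that are clinically significant, or that lead to interruption, discontinuation or corrective therapy, are recorded as AEs or SAEs and so reach the AE tables. The SAP also plans a listing of subjects with any PCS result and listings of all laboratory values, and the data monitoring committee reviews unblinded data (Protocol 5.3). None of these gives the missing number and percentage, but together they rule out saying that an excess would go unseen.

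A third objection is that power is the wrong yardstick. The laboratory analyses are descriptive, and several listed parameters are clearly related (AST and ALT, total and direct bilirubin, hemoglobin and hematocrit, INR and prothrombin time), so independence is unrealistic. This also stands.

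**Conclusion.** The point holds as a gap in specification. On the natural reading of the endpoint, following the placebo-controlled SAP as written does not produce the laboratory component, and the tables it does produce cannot be converted into it. That conclusion rests on the text and on the bounds above, not on assumed rates.

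Its reach is limited. A reader might take the gap to affect the whole primary safety endpoint; it concerns one of four components, the others being deaths, SAEs and AEs leading to discontinuation. A reader might also take the 6% against 70% contrast as the size of the problem. The documents do not support that: it assumes independent parameters with risk doubled in every one, and the advantage reverses when the excess sits in a single parameter. No document figure is wrong on the missing row, and the count remains derivable from planned listings. If the sponsor intends the per-parameter reading, the SAP should say so, since the present wording leaves the unit of a primary safety component open.

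**What to change.** In the Grade analyses part of Section 6.3.2 of the placebo-controlled SAP, add one row by safety treatment group: subjects with at least one post-baseline Grade 3 or 4 value in any scheduled gradable parameter (n, %), with Grade 4 also shown separately. Take as denominator the subjects with at least one post-baseline evaluation, which is the section's existing rule. State that this row reports the laboratory component of the primary safety endpoint.

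Keep the per-parameter tables alongside it, because they are the more sensitive display for a toxicity confined to one parameter.

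Before programming the row, check the corrected-calcium formula against the source document and correct it if it reads as printed. Applied literally, it would place nearly every subject's calcium far below the normal range. A parameter table confines that error to calcium, but a pooled row would be swamped by it.

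The cost is a few sentences in the SAP, one table row and one formula check, with no new data. It should be settled before unblinding.

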4. STUDY OBJECTIVES AND ENDPOINTS

Objective	Endpoint
Primary	
To evaluate the efficacy of BIIB092, compared to placebo, as measured by a change from baseline in the PSP Rating Scale (PSPRS) at Week 52.	The primary efficacy endpoint will be evaluated by comparing the change from baseline in the total PSPRS score at Week 52 in participants treated with BIIB092 relative to the change in the total PSPRS score in participants treated with placebo.
To assess the safety and tolerability of BIIB092, relative to placebo, by measuring the frequency of deaths, SAEs, and AEs leading to discontinuation, and Grade 3 & 4 laboratory abnormalities.	The primary safety endpoint will be evaluated by tabulating the numbers and percentages of deaths and unique participants with SAEs and AEs leading to discontinuation, and Grade 3 & 4 laboratory abnormalities.
Key Secondary	
To evaluate the efficacy of BIIB092, compared to placebo, as measured by a change from baseline in the Movement Disorder Society-sponsored revision of the Unified Parkinson's Disease Rating Scale (MDS-UPDRS) Part II at Week 52.	The impact of BIIB092 on the MDS-UPDRS Part II will be evaluated relative to the change from baseline at Week 52 in the BIIB092-treated participants and compared to that of the placebo-treated participants.
To evaluate the efficacy of BIIB092, compared to placebo, as measured by the Clinical Global Impression of Change (CGI-C) at Week 52.	The impact of BIIB092 on the CGI-C scale score will be evaluated at Week 52 in the BIIB092-treated participants and compared to that of the placebo-treated participants.
To evaluate the efficacy of BIIB092, compared to placebo, as measured by a change from baseline in the Repeatable Battery for the Assessment of Neuropsychological Disease Severity (RBANS) at Week 52.	The impact of BIIB092 on the RBANS scale will be evaluated relative to the change from baseline at Week 52 in the BIIB092-treated participants and compared to that of the placebo-treated participants.
To assess the impact of BIIB092 on quality of life, relative to placebo, as measured by change from baseline on the Progressive	The impact of BIIB092 on the PSP-QoL will be evaluated relative to the change from baseline at Week 52 in the BIIB092-treated

CONFIDENTIAL

The information contained herein may not be used, disclosed, or published without the written consent of Biogen MA Inc.

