6.2.3. Physical and Laboratory Test Findings

1. Evidence of organ dysfunction or any clinically significant deviation from normal in physical examination, vital signs, ECG, or clinical laboratory determinations beyond what is consistent with the target population.
2. Clinically significant abnormality on 12-lead ECG prior to study treatment administration, confirmed by repeat.
3. Total bilirubin, alanine aminotransferase (ALT), or aspartate aminotransferase (AST) greater than 2 times the upper limit of normal (ULN), confirmed by repeat. Elevated total bilirubin suspected to be due to Gilbert syndrome should be discussed with the Medical Monitor.
4. Serum creatinine $>168 \text{ mol/L}$ (1.9 mg/dL), confirmed by repeat.
5. Hematocrit $<30\%$, absolute neutrophil cell count of $\leq 1500/\mu\text{L}$ (with the exception of a documented history of a chronic benign neutropenia), or platelet cell count of $<120,000/\mu\text{L}$, or International normalized ratio (INR) >1.4 or other coagulopathy, confirmed by repeat. (Note: Participants with INR >1.4 due to antiplatelet/anticoagulant medications are eligible.)
6. A clinically significant abnormal thyroid-stimulating hormone test.
7. [REDACTED]
8. Hemoglobin A1C (HbA1C) $>8\%$, confirmed by repeat.

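### The primary Grade 3/4 laboratory table sets no condition on baseline grade, so a pre-existing Grade 3/4 value that recurs after dosing counts as an event

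*SAP*

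**What the plan says.** Protocol Section 4 evaluates the primary safety endpoint by "tabulating the numbers and percentages of deaths and unique participants with SAEs and AEs leading to discontinuation, and Grade 3 & 4 laboratory abnormalities". It does not mention baseline grade and sets no test or margin.

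The placebo-controlled SAP implements the laboratory part in Section 6.3.2 under Grade analyses. Each scheduled parameter is summarised by its worst CTCAE grade after baseline, and the SAP states that "this analysis includes the primary endpoints of Grade 3 and 4 laboratory abnormalities". The inclusion rule is: "Subjects need to have at least one post-baseline evaluation in order to be included in the analysis".

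Two neighbouring analyses in Section 6.3.2 are stricter. The shift tables also require "a baseline value either unknown or not low/high/abnormal in order to be included in the analysis". The PCS tables require subjects "to have at least one post-baseline evaluation and a baseline value not PCS (including missing) in order to be included in the analysis". Section 6.2.1 counts an adverse event only if it began or got worse once dosing had started.

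Protocol Section 6.2.3 sets numeric entry limits for bilirubin, ALT, AST, creatinine, hematocrit, neutrophils, platelets, INR and HbA1C. There are exceptions: documented chronic benign neutropenia is accepted, and "Participants with INR >1.4 due to antiplatelet/anticoagulant medications are eligible".

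**The concern.** A safety table meant to show laboratory toxicity should separate values that became severe on treatment from values that were severe beforehand. Three other parts of the plan make that separation. The table carrying the primary laboratory endpoint does not, and no reason is given.

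Pre-existing cases that recur add events to both arms that have nothing to do with the drug. A reader of the planned table could not tell whether a between-arm difference reflects new abnormalities or an uneven spread of old ones.

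**Working it through.** **Plan figure.** The plan states no rate, margin or power for this endpoint, so there is nothing to reproduce. The one design figure, 80% power in Protocol Section 17.1, concerns the PSPRS comparison. It reproduces (80.2% by noncentral t with 115 and 230 completers, difference 3.2, SD 9.95, two-sided 0.05) but has no bearing here.

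**Rules side by side (placebo-controlled SAP).**

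| Analysis | Treatment of pre-existing abnormality |
|---|---|
| Adverse events, 6.2.1 | counted only if new or worse after dosing starts |
| Shift, 6.3.2 | subject left out if already abnormal |
| PCS, 6.3.2 | subject left out if already PCS; missing baseline kept |
| Grade 3/4 (primary), 6.3.2 | no condition |

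**Formula.** For one parameter, let b be the share already Grade 3/4 at baseline (equal in both arms), q the probability that the grade is seen again after dosing, and p0, p1 the new-onset risks on placebo and BIIB092. The counted risk is P = bq + (1 − b)p. Hence the risk difference is (1 − b)(p1 − p0), and the ratio moves toward 1 when bq > 0.

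**Numbers.** The documents give none of b, q, p0 or p1; all values below are assumptions.

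| p0, p1 | b | q | P0 | P1 | Ratio | Difference (points) |
|---|---|---|---|---|---|---|
| 2%, 4% | 0 | – | 2.00% | 4.00% | 2.00 | 2.00 |
| 2%, 4% | 0.5% | 1 | 2.49% | 4.48% | 1.80 | 1.99 |
| 2%, 4% | 1% | 1 | 2.98% | 4.96% | 1.66 | 1.98 |
| 2%, 4% | 3% | 1 | 4.94% | 6.88% | 1.39 | 1.94 |
| 2%, 4% | 1% | 0.5 | 2.48% | 4.46% | 1.80 | 1.98 |
| 1%, 3% | 1% | 1 | 1.99% | 3.97% | 1.99 (from 3.00) | 1.98 (from 2.00) |

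Worked row (b = 1%, q = 1): P0 = 0.01 + 0.99 × 0.02 = 0.0298; P1 = 0.01 + 0.99 × 0.04 = 0.0496; ratio 0.0496/0.0298 = 1.66.

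**Chance imbalance.** With 153 and 306 subjects, the SD of the arm difference in baseline prevalence is √[b(1 − b)(1/153 + 1/306)]. This is 0.99 points at b = 1% and 1.39 points at b = 2%. At b = 1% and q = 1, one SD either way turns a counted difference of 1.98 points into roughly 1.0 or 3.0. It would also produce about 1 point with no drug effect. One placebo subject is 1/153 = 0.65 points.

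**What other outputs show.** PCS Table 9 contains no INR, prothrombin time, magnesium or creatine kinase. A subject whose INR is already high at baseline is left out of the shift-to-high count. For that subject the grade table is the remaining categorical comparison between arms, and it cannot distinguish worsening from a stable value.

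**Side check on calcium.** Calcium is graded after albumin correction. As printed, calcium 2.4 mmol/L with albumin 40 g/L gives ¼ × [2.4 − 0.8 × (4 − 4)] = 0.60 mmol/L, far below the SAP's PCS-low limit of 2 mmol/L. With the calcium term multiplied by 4 inside the bracket the result is 2.4. The factor may have been lost in text conversion.

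**The case against.** The case for leaving the table alone has weight. The SAP follows the protocol, which asks for numbers and percentages and says nothing about treatment emergence, and the placebo arm supplies a background rate. The endpoint is tabulated, not tested. Entry limits should make baseline Grade 3/4 uncommon for several parameters. Changes from baseline by visit, shift tables, PCS counts and listings give some baseline-referenced information. All of this stands, and it keeps the point small.

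Four stronger readings are tempting but unsupported.

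- **That the rule dilutes any drug effect.** The ratio moves toward 1 on average, but the difference, which a table of percentages displays, shrinks only by the factor (1 − b). Imbalance can also inflate the contrast.
- **That every subject with baseline Grade 3/4 becomes a case.** Only grades after baseline count. A subject whose value improves stays in the denominator alone.
- **That context-free grading adds cases.** The sentence "Grade determination is based solely on laboratory values and does not take other clinical information into account" may look like support, but the SAP goes on to warn that higher grades may be under-counted.
- **That the entry exceptions are themselves Grade 3/4.** The documents give no CTCAE cut-offs, so they do not show that a raised INR on anticoagulants or benign neutropenia reaches those grades. The exceptions show only where the issue could arise.

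The objection does not explain why this one table departs from the SAP's own practice, and the other outputs do not fully close the gap for INR, magnesium or creatine kinase.

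**Conclusion.** The point holds as an internal inconsistency of modest size. The primary Grade 3/4 laboratory table can count an abnormality that was present before dosing and never worsened. Under the illustrative 1% prevalence with full recurrence, a per-parameter ratio of 2.0 reads as 1.66 and the difference is almost unchanged at 1.98 points. The larger practical risk is an uneven split of pre-existing cases between arms of 306 and 153, which can hide or mimic a signal and which the planned table cannot reveal.

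If baseline Grade 3/4 is absent for a parameter, nothing changes. The point matters mainly for INR on antiplatelet or anticoagulant medication, neutrophils in chronic benign neutropenia, and parameters with no numeric entry limit, such as electrolytes, lymphocytes and creatine kinase. It is a cheap improvement and does not invalidate the safety analysis.

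**What to change.** In placebo-controlled SAP Section 6.3.2, for the primary safety table:

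- Count a Grade 3/4 value after baseline only when its grade is worse than the baseline grade in the same direction, or when baseline is missing. A move from Grade 3 to Grade 4 still counts. State the denominator. If all subjects stay in it, the 1% example gives 0.99 × 4% = 3.96% versus 0.99 × 2% = 1.98%, a ratio of 2.00.
- Add a table of baseline grade by worst grade after baseline, by arm.
- Keep the current all-subjects table as supportive.
- Check the corrected-calcium formula against the source before deriving baseline calcium grades.

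Baseline is already defined in Section 3.1 and collected, so the cost is one sentence, one programming flag, one extra table and the formula check. The small downside is a slightly lower event count.
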